6.4.1. Infusion Monitoring

Subjects will be monitored in the ICU for two hours prior to infusion to establish baseline vital signs (oxygen saturation, heart rate, respiratory rate, blood pressure, and temperature) every 15 minutes. Monitoring will also continue throughout the infusion.

Once the infusion is begun, 2L/min oxygen via nasal cannula will be provided if the oxygen saturation drops below 90% on room air. The infusion will be stopped if the oxygen saturation does not return to >93% within 3 minutes of initiating supplemental oxygen or if the subject requires greater than 2L/min supplemental oxygen to achieve the required saturation of >93%. If a subject requires the addition of oxygen, it will be continued for 4 hours after the completion of the infusion. At that time, oxygen will be weaned off to maintain a saturation >93% on room air.

6.5 Concomitant Therapy

6.5.1 Permitted therapy

Concomitant medications will be recorded on the case report form (CRF), which includes all FDA-approved medications, therapies, and dietary supplements.

6.5.2 Excluded therapy

Medications and therapies not approved by the FDA are prohibited for the duration of this trial, including participation with any investigational drug or device.

6.5.3. Subject monitoring

All aspects of the study will be conducted in accordance with Good Clinical Practice (GCP) as described in the ICH Guideline (CFR ICH Selected Regulations and Guidance for Drug Studies, CFR Title 21 Food and Drugs Revised as of April 1, 2002) all applicable national and local regulations. Monitoring will be conducted by a qualified outside source at the study site.

Monitoring of key safety endpoints will be conducted. If rates significantly exceed the pre-set threshold, then the DSMB will be advised.

6.6 Blinding and Unblinding

Subjects will be randomized into active groups. Only designated technicians in the ISCI Cell Processing Laboratory will be unblinded to treatment. The investigator, study staff, subject and anyone involved in the care of the subject will not be made aware of the assigned treatment regimen. Before dispensing the investigational product, Cell Therapy Lab staff will confirm the CMV status of eligible recipient. This information will be used to select Allo- MSC product. CMV status of the recipient and donor of the Allo-MSC product will be matched. CMV positive Allo-MSC product will only be infused to a CMV positive recipient. All CMV negative recipients will receive CMV negative Allo-MSC product⁹¹.

The designated cell-processing technicians will prepare both the allogeneic hMSCs infusions. The investigational agent infusions will be prepared in identical infusion bags and labeled with the identical investigational drug labels. A brown plastic slip cover will be placed over the infusion lines as well as the bags to maintain the blind. The designated technicians in the ISCI Cell Processing Laboratory (or designee) will be responsible for maintaining the investigational product records including randomized treatment assignments by subject identification.

If for important medical reasons unblinding is thought to be necessary, the Investigator may identify the treatment assignment by obtaining the randomization assignment by contacting the Director of the Cell Manufacturing Program at ISCI who is responsible for maintaining randomization records for all subjects.

6.7 Study Investigational Therapy Management

6.7.1 Investigational Product Labeling and Storage

The product label contains the elements required by the CFR and other national and local authorities for investigational products. ISCI GMP Cell Processing Facility (CPF) will

directly store and deliver the designated cell processing technologist in the CPL/CPF, and will be kept cryopreserved in liquid nitrogen vapor phase until shortly before administration must be stored in a securely locked enclosure. Access is strictly limited to unblinded CPL/CPF personnel prior to preparation for infusion. After preparation for infusion, the Investigator and his or her designees are permitted to administer the Investigational Product to subjects participating in this protocol.

6.7.2 Investigational Product Accountability Procedures

In accordance with all applicable regulatory requirements, the Cell Processing Laboratory/Cell Processing Facility will maintain a record of the investigational products hMSCs received, dispensed, administered, destroyed, or returned. The final disposition of all unused, empty, and partially used Cryocyte™ bags will be handled in accordance with the drug preparation manual. An independent unblinded clinical research associate (monitor) or auditor will perform compliance monitoring during the study.

Only unblinded personnel may access accountability records until the study blind has been broken.

7. STUDY PROCEDURES

7.1. Time and Events Schedule

The Time and Events Schedule for the conduct of this study is shown in Table 2

Schedule of Assessments

Table 2: Time and Events Table for Pilot and Randomized Phases

VISIT	Screening Day -56 ± 28 days	Baseline (-4 weeks)	Day 1	Week 2 (Day 14) +/- 2 days	Month 1 (Day 30) (+/-2 weeks)	Month 3 (Day 90) (+/-2 weeks)	Month 6 (Day 180) (+/-2 weeks)	Month 12 (Day 365) (+/-2 weeks)
Informed Consent	x							
Full Medical History	x							
Physical Exam	x	x	x	x	x	x	x	
12-lead (ECG)	x	x	x	x	x	x	x	
Concomitant Medications	x	x	x	x	x	x	x	x
Mini Mental State Examination (MMSE)	x						x	
Randomization		x						
Infusion Treatment (IP)			x					
Dobutamine Stress Echo Test (DSE)	x						x	
Bone Density Scan (DEXA) ⁸		x					x	
FEV-1		x				x	x	
6 Minute Walk Test		x				x	x	
4 Meter Gait Speed Test ⁷		x				x	x	
SPPB Assessment		x				x	x	
Dynamometer (handgrip) ¹⁰		x				x	x	
Smell Identification Test (UPSIT)		x				x	x	
IIEF, SQOL-F Questionnaires		x			x	x	x	
QOL Questionnaires (ICECAP, EQ-5D, SF-36,CHAMPS, MFI)		x			x	x	x	
Questionnaires (Subject and Physician Global Assessment ⁹)							x	
Urinalysis	x				x	x	x	
Hemat., Chem., CBC, LFTs, INR, and other labs ¹	x		x	x	x	x	x	
HIV 1, HIV 2, Hep. B & C, and CMV	x							
Serum or Urine Pregnancy Test ²	x		x					
Review Adverse Events			x	x	x	x	x	x
Immune Monitoring ⁴			x	x	x	x	x	
Biomarker Assessment ³			x				x	
Optional: Brachial Ultrasound ⁵		x				x		
Optional: Endothelial blood samples ⁶		x				x		

Time and Events Table Key:

1 – The minimal laboratory requirements for hematological, liver function and renal function include:

Hematology Tests: white blood cell count, platelet count, hemoglobin and hematocrit.

Liver Function Tests: Albumin, alkaline phosphatase, alanine transaminase, aspartate aminotransferase, prothrombin time / activated partial thromboplastin time, and bilirubin(fractionate if total >1.5 times normal).

Renal Function Tests: creatinine, creatinine clearance, blood urea nitrogen (BUN), glomerular filtration rate, sodium, potassium, chloride, calcium, carbon dioxide, and glucose.

Serum Uric Acid, Pro-BNP, and C-reactive protein (CRP), IL6, fibrinogen, D-Dimer, DNA, TNF α , testosterone (males only) and estrogen (females only).

2 – A serum or urine pregnancy test will be completed within 36 hours prior to infusion for females of childbearing potential.

3 – The following biomarkers will be analyzed:

- **Cell-surface markers:** CD19, CD27, IgD, and CD5 (for Switched Memory, Naïve, Late/Exhausted, IgM memory B cells and regulatory B cells); CD19 and intracellular TNF- α (to assess intracellular TNF- α); CD3, CD4, CD8, CCR7 and CD45RA (for Central Memory, Naïve, Effector Memory, TEMRA T cells and CD4 to CD8 ratio); CD3, CD25 and FOXP3 (to assess regulatory T cells)
- **Transcriptomic/Proteome:** RNA, miRNA, protein samples, and telomerase, akt
- **Growth factors:** Sdf-1, notch,
- **Functional Assays:** cell growth rate, VEGF, and CFU assay

4 – Immune monitoring for graft rejection. Calculated panel reactive antibodies will be performed from the serum of the subjects on day 1 and 6 months post treatment. In addition, the following cell surface markers will be used to assess for activated T-cells based upon a CD3 $^+$ CD25 $^+$ (late/chronic T cell activation) or CD3 $^+$ CD69 $^+$ phenotype (early T cell activation).

5 – Optional brachial ultrasound to assess endothelial function.

6 – Optional: An additional 5 lavender top tubes (EDTA) will be drawn to assess the ability of endothelial progenitor cells to form colonies.

7 – 4 meter gait speed test will be performed twice per visit and the average of the exams will be taken.

8 – DEXA scan will be performed at baseline and Month 6. The scans of the hip and spine for bone density, and total body composition will be assessed at both visits.

9 – Subject and Physician Global Assessments are not applicable to pilot subjects in the initial infusion of the trial.

10 – Dynamometer will be performed at least three (3) times during each applicable visit for each hand. The three values collected will be averaged for each hand. (Please reference the instruction manual on how to administer.)

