Definition of Endpoints	
Safety (Primary): Incidence (at one month post-infusion) of any treatment-emergent serious adverse events (TE-SAEs), defined as the composite of: death, non-fatal pulmonary embolism, stroke, hospitalization for worsening dyspnea and clinically significant laboratory test abnormalities determined per the Investigator's judgment.
 
Efficacy (Secondary): During the screening, baseline, Month 3 and/or Month 6 visits.
 
 • Difference in rate of change of frailty defined as: 
 - Reduced Activity (assessed via CHAMPS questionnaire) - Slowing of Mobility (assessed via gait speed test and SPPB assessment) - Weight Loss - Diminished handgrip strength (assessed via dynamometer) - Exhaustion (assessed via the MFI questionnaire) - Decrease in subject quality of life assessment(s) (assessed via ICECAP, SF-36, EQ-5D Questionnaires) • Death from any cause. • Change between screening and 6 months in dobutamine stress echo induced ejection fraction • Change between screening and 6 months in the following panel of inflammatory markers: CRP, IL-6, D-dimer, fibrinogen, CBC with differential, and TNFα
Safety (Additional)	
 • During the 12 week follow-up period and each consecutive time-point up until the final visit
Inclusion Criteria (Applicable for Main Phase of the trial; reference each individual addendum for its inclusion criteria)	
 1. Provide written informed consent. 2. Subjects age ≥ 60 and ≤ 95 years at the time of signing the Informed Consent Form. 3. Show signs of frailty apart from a concomitant condition as assessed by the Investigator with a frailty score of 4 to 7 using the Canadian Clinical Frailty Scale. 4. Female subjects must have an FSH ≥ 25.8 mIU/mL, if not currently on hormone replacement therapy.
Exclusion Criteria (Applicable for Main Phase of the trial; reference each individual	
 1. Score of <24 on the Mini Mental State Examination (MMSE) 2. Be a female who is pregnant, nursing, or of childbearing potential while not practicing effective contraceptive methods. Female subjects must undergo

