2.2.2 Secondary Endpoints (Efficacy)

The following efficacy endpoints will be evaluated in this trial (During the screening, baseline, Month 3 and/or Month 6 visits):

1. Difference in rate of decline of Frailty defined as:
 - a. Reduced Activity (assessed via CHAMPS questionnaire)

- b. Slowing of Mobility (assessed via a 4 meter gait speed test and SPPB assessment)
- c. Weight Loss
- d. Diminished handgrip strength (assessed via dynamometer)
- e. Exhaustion (assessed via the MFI questionnaire)
- f. Decrease in subject quality of life assessment(s) (assessed via ICECAP, SF-36, EQ-5D Questionnaires)

2. Death from any cause.
3. Change between screening and 6 months in dobutamine stress echo induced ejection fraction.
4. Change between screening and 6 months for the following panel of inflammatory markers: CRP, IL-6, D-dimer, fibrinogen, CBC with differential, and TNFa

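### Endpoint 4 takes its reference only from a screening draw 28 to 84 days before infusion, although the same inflammatory markers are scheduled again on Day 1 at a time of day that the protocol does not fix

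*Combined protocol and SAP*

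**What the plan says.** Section 2.2.2, item 4, defines the endpoint as "Change between screening and 6 months for the following panel of inflammatory markers: CRP, IL-6, D-dimer, fibrinogen, CBC with differential, and TNFa". The synopsis uses the same reference. Neither names another reference visit, an average or a covariate, and section 9 defines no baseline for laboratory values.

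Table 2 heads its first column "Screening Day -56 ± 28 days". The laboratory row, "Hemat., Chem., CBC, LFTs, INR, and other labs", is marked at Screening, Day 1, Week 2 and Months 1, 3 and 6. Key 1 spells out the other labs as "Serum Uric Acid, Pro-BNP, and C-reactive protein (CRP), IL6, fibrinogen, D-Dimer", with TNF-alpha later in the same line, and restricts none of these to particular visits. Section 3.2 agrees on the visits (every clinic visit except Baseline and Month 12) and describes these tests as safety tests.

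One component is less clear. Endpoint 4 includes a differential count, but the minimal hematology set in Table 2 key 1 is "white blood cell count, platelet count, hemoglobin and hematocrit". Section 8.2 does list the differential.

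**The concern.** A single laboratory value is a noisy reference, and this one may be up to 12 weeks old at infusion. With 10 subjects per arm, error in the reference is a sizeable part of the error in each marker comparison. The change called six-month also includes 4 to 12 weeks before any treatment. A second draw of the same five markers is already scheduled on the day of infusion. If it is taken before anything is given, it is closer to treatment and could reduce the noise without a further sample. At stake are the precision and recency of the reference for the inflammation endpoint, which bears on the inflammation aims in sections 2.1.1 and 2.1.2.

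**Working it through.** The plan states no power, SD or correlation for this endpoint, so there is no figure of its own to reproduce.

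**Timing, from Table 2 (infusion taken as day zero)**
- Screening: -56 - 28 = -84 to -56 + 28 = -28, so 28 to 84 days before infusion.
- Month 6 is Day 180 with a window of 2 weeks. The interval covered by the endpoint runs from (180 - 14) + 28 = 194 days to (180 + 14) + 84 = 278 days.

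**Is the Day 1 laboratory draw before treatment?**
- Pointing that way: section 7.2.8 takes the Day 1 immune-monitoring blood before infusion. Key 2 requires the pregnancy test, marked in the Day 1 column, within 36 hours before infusion. The biomarker row is marked only on Day 1 and at Month 6, so Day 1 is its only possible reference.
- Silent: Table 2, key 1, section 7.2.3 and Appendix 1 do not time the laboratory row against infusion. Appendix 1 also gives intravenous hydrocortisone and diphenhydramine 30 minutes to an hour before infusion, and the laboratory row is not timed against that either.
- Conclusion: plausible, not established. The figures below apply only if the draw comes first.

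**Change score, in units of one draw's variance**

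Assume equal SDs. Let *a* be the correlation of Screening with Day 1, *b* of Screening with Month 6, and *c* of Day 1 with Month 6. None of these is in the documents.
- Screening alone: 2(1 - b).
- Mean of the two draws: 1 + (1 + a)/2 - (b + c).

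| Assumption | Screening alone | Mean of two | Cut |
|---|---|---|---|
| a = b = c = r | 2(1 - r) | 1.5(1 - r) | 25% |
| a = 0.7, b = c = 0.5 | 1.00 | 1 + 0.85 - 1.00 = 0.85 | 15% |
| a = 0.8, b = c = 0.5 | 1.00 | 1 + 0.90 - 1.00 = 0.90 | 10% |
| a = 0.7, b = 0.5, c = 0.6 | 1.00 | 1 + 0.85 - 1.10 = 0.75 | 25% |

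A 25% cut makes the standard error 1 - √0.75 = 13% smaller, equivalent to 10/0.75 = 13.3 subjects per arm instead of 10. A 15% cut is equivalent to 10/0.85 = 11.8 per arm, and a 10% cut to 10/0.90 = 11.1.

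**Covariate adjustment, residual variance with common correlation r**

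One draw: 1 - r². Two draws: 1 - 2r²/(1 + r).

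| r | One | Two | Cut |
|---|---|---|---|
| 0.3 | 0.910 | 0.862 | 5% |
| 0.5 | 0.750 | 0.667 | 11% |
| 0.7 | 0.510 | 0.424 | 17% |
| 0.9 | 0.190 | 0.147 | 22% |

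If the early draws are more alike, the cut shrinks here too. With b = c = 0.5, a = 0.7 gives 1 - 0.5/1.7 = 0.706 against 0.750 (6%), and a = 0.8 gives 1 - 0.5/1.8 = 0.722 (4%).

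**The case against.** A single screening reference is legitimate. It matches endpoint 3, which also runs from screening to Month 6, and it avoids infusion-day conditions. Section 9.2 calls the efficacy outcomes exploratory and presents continuous variables descriptively, and section 9.1 sets no power target, so no stated claim fails. That stands and limits the weight of the point. It does not show that one older draw is as good as two.

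A reader might infer that the plan throws away a pre-treatment value already in hand. The documents do not support this. The time of the Day 1 laboratory sample is not given, and section 3.2 uses these values for safety; they are unused only as a reference for endpoint 4. A sample taken after hydrocortisone or after infusion would not be a clean second reference.

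A reader might also take the 25% as general. It holds for every r only under equal correlation, and draws 4 to 12 weeks apart may well resemble each other more than either resembles Month 6. Part of the gain is also available otherwise: at r = 0.5, adjusting for screening alone already gives 0.75, the same as the change from a two-draw mean.

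Nor does the point show bias between arms. All randomized arms share the same screening window.

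The addenda repeat the endpoint and mark the same two draws. However, their screening windows differ (Table A1 allows 6 months either way; Tables B1, C1 and D1 use 45 days), and they have no concurrent control, so the 28 to 84 day figure and the per-arm argument do not carry over.

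**Conclusion.** The point holds in limited form. Endpoint 4 relies on one draw 28 to 84 days before infusion, while CRP, IL-6, fibrinogen, D-dimer and TNF-alpha are scheduled again on Day 1 and otherwise serve only safety. Provided the Day 1 sample precedes premedication and infusion, using both draws would cut change-score variance by 25% under equal correlation, and by about 10% to 15% if the early draws correlate 0.8 to 0.7 with each other and 0.5 with Month 6. With covariate adjustment the cut is about 5% to 22% for r = 0.3 to 0.9, and about 4% to 6% in the less favourable cases shown. These sizes rest on assumed correlations and equal SDs. This is a cheap improvement to an exploratory secondary endpoint, with no effect on the primary safety endpoint.

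**What to change.** For the randomized phase:

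1. State in Table 2 that the Day 1 laboratory panel is drawn before premedication and infusion, and record the draw time.
2. In section 2.2.2 and the synopsis, define the endpoint 4 reference as the mean of the Screening and Day 1 values, on the log scale for the five named markers, or enter both as covariates.
3. Where a Day 1 draw before premedication is not documented, use the screening value alone for that subject.
4. Do not log-transform differential counts, which can be zero, and make Table 2 key 1 agree with section 8.2 on whether the differential is measured.
5. For subjects already treated, label the analysis with the new reference as post hoc.

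The cost is endpoint wording and one line on draw timing, with no added sample, visit or subject. The downside is that subjects may differ in the number of reference draws, so the report should give the count with one and with two, and show the screening-only result alongside.

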7.2 Study Phases and Visits

7.2.1 Screening Visit

See Table 2 for the procedures and assessment to be performed during the screening visit of the study. Screening visit test and procedures will begin upon the subject signing the informed consent form (ICF). No screening exams will take place until the subject is fully informed of the research and signs the consent form. The tests will take place over several days and will need to be completed prior to the subject starting the baseline visit.

Physical exam

A complete physical examination will include general appearance, skin, head and neck, Lymph nodes, musculoskeletal/extremities, cardiovascular, chest/lungs, abdomen, and neurological assessment. At screening information about the physical examination and any significant findings must be recorded in the source documentation at the study site. Weight should be measured at each physical exam on a calibrated scale with the subject wearing only light clothing and no shoes. Height (in bare feet or wearing only thin socks) will be measured at the Screening visit.

Vital signs

Vital sign measurements will be performed at least once on each study visit up to time of discharge. These measurements will consist of respiratory rate, heart rate, blood pressure, and temperature. Respiratory rate, heart rate, and blood pressure should be measured in a sitting position after 5 minutes of rest.

Dobutamine Stress Echocardiography (DSE)

A Dobutamine Stress Echocardiography will be performed twice during the study, once at screening and at the Month 6 follow-up visit. This exam will assist in mimicking the effect of exercise on subjects to assess the heart muscle when under stress to better evaluate ejection fraction in frail subjects. Guidelines for completing the (DSE) are outlined in Appendix 2 of this protocol.

7.2.2 Baseline Visit

See Table 2 for the procedures and assessment to be performed during the baseline visit of the study. Once all screening exams are completed and it has been determined that the subject remains eligible for the study, subjects will be enrolled into the study. The baseline visit will take place within four weeks from treatment. The listed procedures should all be performed as soon as practicable.

Bone density Dexa scan will be performed at the baseline visit (if not done within three months prior to enrollment).

The Smell Identification Test (UPSIT) test will be performed once at baseline and once at the Month 3 and Month 6 follow-up visits. Age-related olfactory dysfunction is felt to be due to cumulative inflammatory damage affecting the olfactory mucosa. The Smell Identification Test (UPSIT) is a self-administered 40-item olfactory test. It provides an absolute indication of smell loss (anosmia, mild, moderate, or severe microsomia) as well as an index to detect malingering.

Endothelial function (Optional Assessments) will occur upon the subject signing the optional section of the informed consent form (ICF). No endothelial function tests will take place until the subject is fully informed of the research and signs the optional portion of the consent form.

- Brachial ultrasound testing and blood collection will be performed to assess endothelial function in the aging frailty population at baseline and 3 months post stem cell infusion. This will help provide cumulative data in assessing whether or not stem cell infusion improves endothelial function.
- Flow Mediated Diameter percent change (FMD%): All measurements of the brachial artery diameter and FMD will be performed in the morning, in a quiet and dark room and at controlled ambient temperatures between 20°C and 26°C. Studies will be conducted after an overnight fast of at least 10 hours (water is permitted), with the subjects supine and after 10 minutes of rest. The subject's right arm will be comfortably immobilized in an extending position, allowing for ultrasound scanning of the brachial artery 5–10 cm above the antecubital fossa. In each examination, recording of vessel images will be followed by inflation of a cuff to supra-systolic pressure (40 to 50 mmHg above systolic pressure) for 5 minutes. Then the cuff will be deflated and the brachial artery diameter will be imaged and recorded for 3 minutes. FMD% more than 10% is considered a normal response. Lower than 10% FMD% reflects endothelial dysfunction, which means a high likelihood to develop cardiovascular event in the future. Subjects with negative FMD% results (the artery is constricted after stress and not dilated as was expected) have the worst prognosis.

- Blood drawn from fasting subjects will be separated and the serum will be frozen until processed as one batch towards the end of the study. Blood will be processed twice – in the beginning of the study and after 3 months.
- Biochemical analysis: soluble pro inflammatory cytokines (interleukin-1, interleukin-6, interleukin-10, VEGFR2, TNF-a).
- Assay of colony forming units: Fresh blood will be processed for cell culture assays for endothelial progenitor stem cells colonies counting (a 5 days' protocol). Fifty milliliter of blood will be processed; peripheral-blood mononuclear cells will be isolated by Ficoll density-gradient centrifugation, will be washed twice in phosphate buffered saline with 5% fetal bovine serum and re-suspended in media (EndoCult basal media with supplements; StemCell Technologies, Vancouver, British Columbia, Canada) for EPC colony-forming assay. Cells will be planted on human fibronectin-coated plates (BIOCOAT; Becton Dickenson Labware, Bedford, Massachusetts) at a density of 5×10^6 cells/well and incubated at 37°C in humidified 5% CO₂. After 48 hours, the non-adherent cells will be re-plated onto fibronectin-coated 24 well plates at a density of 1×10^6 cells/well. After 5 days, colony forming units (defined as a central core of rounded cells surrounded by elongated and spindle-shaped cells) will be counted manually in 8 wells out of a 24-well plate.

